11.1 Ethical Principles

This study will be conducted in accordance with the principles established by the 18th World Medical Association Joint Conference (Helsinki, 1964) and all subsequent revisions.

11.2 Legal and Regulatory Compliance

This study will be conducted in compliance with all applicable laws and regulations.

11.3 Informed Consent

Before any study procedures begin, the potential subject will be informed of the risks and benefits of this study using an informed consent form. The language of the informed consent should be simple and understandable. The informed consent form should clearly state that it is voluntarily signed and specify the risks and benefits associated with participation in this study.

The investigator is responsible for explaining the content of the informed consent to the subject and obtaining a signed and dated informed consent form from the subject or his/her legal representative before the study begins.

11.4 Data Protection

Personal data of patients and investigators in the database of the responsible research unit (Shanghai Pulmonary Hospital) should be processed in accordance with all applicable local laws and regulations.

When archiving or processing personal data related to investigators and/or patients, the responsible research unit (Shanghai Pulmonary Hospital) should take all appropriate measures to protect and prevent unauthorized third parties from obtaining such information.

11.6 Record Keeping

Investigators should arrange for the storage of study documents until the study is completed. In addition, regarding the storage of patient records, investigators should comply with specific local regulations/guidelines.

Unless otherwise stated in the investigator's agreement, it is recommended that investigators keep study documents for at least five years after the completion or termination of the study, in accordance with other standards and/or local laws.

11.7 Early Termination of the Study

The principal investigator of the responsible research organization may decide to terminate this study at any time and for any reason; the decision to terminate the study will be communicated to the participating investigators in writing.

If applicable, the ethics committee (IRB) and health regulatory authorities should be notified in accordance with local regulations.

11.8 Inspections by the Responsible Research Organization and Regulatory Authorities

Investigators agree to allow inspectors from the responsible research organization/inspectors from regulatory authorities direct access to the study records of subjects for review, and understand that these individuals are bound by professional confidentiality principles, and therefore will not disclose any personal identity or personal medical information of patients.

Investigators will make every effort to assist with inspections and visits, enabling inspectors/visitors to have access to all necessary equipment, data, and documents.

During these inspections, the confidentiality of the data and the protection of the subjects should be respected.

Investigators should immediately communicate the results and information provided after regulatory authority inspections with the responsible research organization.

Investigators should take appropriate corrective measures for any issues identified during audits or inspections, as required by the responsible research organization.

12 Study Management

12.1 Access to Original Data/Documents

The data mentioned may not be used without permission from the principal investigator of the responsible research organization.

The principal investigator of the responsible research organization has full access to the final data to enable appropriate academic analysis and reporting of the study results.

12.2 Protocol Amendments

Any amendments to the protocol will be documented in written amendments, signed by the investigators and the responsible research organization. Signed amendments will be attached to this protocol.

Amendments to this protocol may need to be submitted in accordance with local regulations.

Appendix 1: Performance Status Scoring Criteria (ECOG PS)

Activity Score	Description	
0	Asymptomatic, fully active, and able to perform	
	unrestricted activities.	
1	Symptomatic, fully ambulatory, but limited to heavy	
	physical activity, capable of light or sedentary work, such	
	as light household work, office work.	
2	Symptomatic, capable of walking, self-care, but unable	
	to perform any physical activity, more than 50% of	
	waking time is spent awake (daytime bed rest time <	
	50%).	
3	Symptomatic, limited self-care capability, more than	
	50% of waking hours in bed or seated, but not yet	
	bedbound.	
4	Completely disabled, unable to care for self, bedbound.	
5	Death.	

Appendix 2: Formulas for Calculating Creatinine Clearance and Body Surface Area

Creatinine Clearance is calculated using the Cockcroft-Gault formula.

For serum creatinine concentration in units of (mg/dL), the calculation formula is:

Male Creatinine Clearance (mL/min) =(140-Age)×(Weight)^a/(72×Serum Creatinine)

Female Creatinine Clearance (mL/min) = 0.85×(140-Age)×(Weight)^a /(72×Serum Creatinine)0.85×(140-Age)×(Weight)a/(72×Serum Creatinine)

For serum creatinine concentration in units of $(\mu mol/L)$, the calculation formula is:

Male Creatinine Clearance (mL/min) = (140-Age)×(Weight)^a /(0.81×Serum Creatinine)(140-Age)×(Weight)a/(0.81×Serum Creatinine)

Female Creatinine Clearance (mL/min) = 0.85×(140-Age)×(Weight)^a /(0.81×Serum Creatinine)0.85×(140-Age)×(Weight)a/(0.81×Serum Creatinine)

a: Age is in years, and weight is in kg.

Body Surface Area Calculation Formula

Body Surface Area (m^2) = 0.00616 × Height (cm) + 0.01286 × Weight (kg) - 0.1529

Appendix 3: Response Evaluation Criteria in Solid Tumors (RECIST) Version 1.1 (Excerpt)

- 1. Measurability of Tumors at Baseline
- 1.1 Definition

At the baseline, tumor lesions/lymph nodes will be categorized into measurable and non-measurable according to the following definitions:

1.1.1 Measurable Lesions

Tumor lesions: Must have at least one dimension that can be accurately measured (recorded as the longest diameter), with the minimum length as follows:

- CT scan 10 mm (CT scan slice thickness no greater than 5 mm)
- Clinical routine examination instruments 10 mm (if the tumor lesion cannot be accurately measured with a measuring instrument, it should be recorded as non-measurable)
- Chest X-ray 20 mm

Malignant lymph nodes: Pathologically enlarged and measurable, the short diameter of a single lymph node on CT scan must be ≥15 mm (it is recommended that the CT scan slice thickness does not exceed 5 mm). At baseline and follow-up, only the short diameter is measured and followed up.

1.1.2 Non-measurable Lesions

All other lesions, including small lesions (longest diameter <10 mm or pathological lymph node short diameter ≥10 mm to <15 mm) and lesions that cannot be measured. Non-measurable lesions include: meningeal disease, ascites, pleural or pericardial effusion, inflammatory breast cancer, cutaneous/pulmonary cancer lymphangitis, abdominal masses that cannot be

confirmed and followed up by imaging, and cystic lesions.

1.1.3 Special Considerations for Lesion Measurement

Bone lesions, cystic lesions, and lesions that have previously received local treatment need special notation:

Bone lesions:

- 1) Bone scans, PET scans, or plain films are not suitable for measuring bone lesions but can be used to confirm the presence or disappearance of bone lesions:
- 2) Lytic or mixed lytic/blastic bone lesions with a definite soft tissue component, and the soft tissue meet the aforementioned definitions of measurability, and if these lesions can be assessed using sectional imaging techniques such as CT or MRI, then these lesions can be considered measurable lesions.
- 3) Osteoblastic lesions are considered non-measurable lesions.

Cystic lesions:

- 1) Lesions that meet the radiographic definition of a simple cyst should not be considered malignant lesions simply because they are defined as simple cysts; they are neither measurable nor non-measurable lesions.
- 2) If they are cystic metastatic lesions and meet the above definition of measurability, they can be considered measurable lesions. However, if there are non-cystic lesions in the same patient, non-cystic lesions should be prioritized as target lesions.

Locally treated lesions:

Lesions located in areas that have undergone radiotherapy or other local regional treatments are generally considered non-measurable lesions unless there is clear progression of the lesion. The study protocol should describe in detail the conditions under which these lesions are considered measurable lesions.

1.2 Measurement Method Description

1.2.1 Lesion Measurement

In clinical evaluation, all tumor measurements should be recorded in the metric system. All baseline assessments of tumor lesion size should be completed as

close to the start of treatment as possible. This study requires that they must be completed within 28 days before the start of treatment.

1.2.2 Evaluation Methods

The same techniques and methods should be used for the baseline assessment of lesions and subsequent measurements. Except for lesions that cannot be evaluated by imaging and can only be evaluated by clinical examination, all lesions must be evaluated using imaging.

Clinical lesions: Clinical lesions are only considered measurable if they are superficial and have a diameter of ≥10 mm when measured (such as skin nodules). For patients with skin lesions, it is recommended to use color photographs containing a ruler to measure the size of the lesions for archiving. When lesions are evaluated using both imaging and clinical examination, imaging should be preferred whenever possible due to its objectivity and the ability to review it repeatedly at the end of the study.

Chest X-ray: When tumor progression is an important study endpoint, chest CT should be prioritized because CT is more sensitive than X-ray, especially for new lesions. Chest X-ray detection is only applicable when the measured lesion boundaries are clear and lung ventilation is good.

CT, MRI: CT is currently the best available reproducible method for efficacy evaluation. The definition of measurability in this guideline is based on a CT scan slice thickness of ≤5 mm. If the CT slice thickness is greater than 5 mm, the smallest measurable lesion should be twice the slice thickness. MRI may also be acceptable in some cases (such as whole-body scanning).

Ultrasound: Ultrasound should not be used as a measurement method for lesion size. Due to the operator-dependence of ultrasound examinations, there is no repeatability after measurement, and the consistency of technique and measurement between different measurements cannot be guaranteed. If new lesions are detected using ultrasound during the trial period, they should be confirmed using CT or MRI. If consideration is given to the radiation exposure from CT, MRI can be used as a substitute.

Endoscopic and Laparoscopic Examinations: These techniques are not recommended for the objective evaluation of tumors, but they can be used to confirm a Complete Response (CR) when biopsy specimens are obtained. They may also be used to confirm recurrence in trials where the study endpoint is recurrence after CR or surgical resection.

2. Assessment of Tumor Response

2.1 Target Lesion Assessment

- Complete Response (CR): All target lesions disappear, and the short-axis diameter of all pathological lymph nodes (including target and non-target nodules) must be reduced to less than 10 mm.
- Partial Response (PR): The sum of the diameters of target lesions decreases by at least 30% compared to the baseline level.
- Progressive Disease (PD): Compared to the smallest sum of the diameters of all measured target lesions during the entire study, there is an increase of at least 20% relative to this value (if the smallest value at baseline, then use the baseline value as a reference); in addition, there must be an absolute increase of at least 5 mm in the sum of diameters (the appearance of one or more new lesions is also considered as disease progression).
- Stable Disease (SD): The degree of reduction in target lesions does not reach PR, and the degree of increase does not reach PD levels, falling between the two, and the smallest sum of diameters during the study can be used as a reference.

2.2 Notes on Target Lesion Assessment

- Lymph Nodes: Even if the short-axis diameter of lymph nodes identified as target lesions is reduced to less than 10 mm, the actual short-axis diameter corresponding to the baseline should still be recorded during each measurement (consistent with the anatomical plane at baseline measurement). This means that if the lymph node is a target lesion, even if it meets the criteria for complete response, it cannot be said that the lesion has completely disappeared because the short-axis diameter of a normal lymph node is defined as less than 10 mm. In the CRF form or other recording methods, target lymph

node lesions should be specifically recorded at a designated location: for CR, all lymph node short diameters must be less than 10 mm; for PR, SD, and PD, the actual measured values of the target lymph node short diameters will be included in the sum of the target lesion diameters.

- Small to Non-measurable Target Lesions: In clinical studies, all lesions (nodular or non-nodular) recorded at baseline should be recorded again with the actual measurement values in subsequent assessments, even if the lesions are very small (e.g., 2 mm). However, sometimes they may be too small to produce a clear image on CT scans, making it difficult for radiologists to define an exact value and possibly reporting them as "too small to measure." In such cases, it is crucial to record the last known value on the eCRF form. If the radiologist believes the lesion may have disappeared, it should be recorded as 0 mm.

If a lesion is indeed present but is vague and cannot provide an exact measurement, it may be defaulted to 5 mm. (Note: This situation is unlikely for lymph nodes, as they generally have measurable dimensions under normal conditions, or are often surrounded by fat tissue, such as in the retroperitoneal space; however, if such a situation arises where a measurement cannot be given, it is also defaulted to 5 mm). The default value of 5 mm originates from the slice thickness of CT scans (this value does not change with different slice thicknesses of CT). Since the likelihood of the same measurement being repeated is low, providing this default value will reduce the risk of incorrect assessment. However, it must be reiterated that if the radiologist can provide an exact value for the size of the lesion, even if the lesion diameter is less than 5 mm, the actual value must be recorded.

Separated or combined lesions: When non-nodular lesions split into fragmented shapes, the longest diameter of each separated part is added together to calculate the sum of the lesion diameters. Similarly, for combined lesions, they can be distinguished by planes between each combined part, and then their respective maximum diameters are calculated. However, if they are inseparable, the longest diameter should be taken as the longest diameter of the entire fused lesion.

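### Appendix 3 gives conflicting diameters for a target lesion too small to measure; carrying the last size forward can hide a response and delay a call of target-lesion progression

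*Protocol*

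**What the plan says.** Protocol section 7.1.2 bases tumor assessment on the investigator's use of RECIST 1.1 and names Appendix 3 as the method. Appendix 3, section 2.2 deals with target lesions that have become too small for the radiologist to size, and it contains three instructions:

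- Carry forward: "In such cases, it is crucial to record the last known value on the eCRF form".
- Lesion possibly gone: "If the radiologist believes the lesion may have disappeared, it should be recorded as 0 mm".
- Lesion present but indistinct: "If a lesion is indeed present but is vague and cannot provide an exact measurement, it may be defaulted to 5 mm". The reason given for this default is that "providing this default value will reduce the risk of incorrect assessment".

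The same section requires the real measurement whenever one can be given, even below 5 mm.

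Appendix 3, section 2.1 then turns the sum of diameters into a response category. Partial response is: "The sum of the diameters of target lesions decreases by at least 30% compared to the baseline level". Progression is judged against the nadir ("Compared to the smallest sum of the diameters of all measured target lesions during the entire study"). It needs both a relative rise ("there is an increase of at least 20% relative to this value") and an absolute one ("there must be an absolute increase of at least 5 mm in the sum of diameters").

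**The concern.** A lesion that cannot be sized is either judged gone or judged present. The 0 mm and 5 mm sentences between them cover both states, so the carry-forward sentence has no case of its own. It supplies a second value for a lesion that already has one. It is worded as essential, while the 5 mm sentence is only permissive, and nothing ranks them. Two readers can follow the text faithfully and enter different diameters for the same scan.

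The carried-forward value is the older size, entered at the point where the lesion has shrunk most. Because the sum feeds both the response and the progression threshold, the choice of entry can reach ORR, PFS and the primary 1-year PFS rate.

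**Working it through.** The protocol states no figure on this point, so there is none to reproduce. The check applies the section 2.1 thresholds to the section 2.2 entries. **All lesion sizes below are assumptions.**

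**Formulas.** Let S0 be the baseline sum and N the smallest sum so far.
- Partial response if S ≤ 0.70 × S0.
- Target-lesion progression if S ≥ max(1.2 × N, N + 5 mm).

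**Illustration.** The baseline is 40 + 25 = 65 mm. At week 6 the larger lesion measures 28 mm and the other is present but cannot be sized.

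| | Last value (25 mm) | 5 mm default |
|---|---|---|
| Sum | 28 + 25 = 53 mm | 28 + 5 = 33 mm |
| Change from baseline | 53/65 − 1 = −18.5% | 33/65 − 1 = −49.2% |
| Category | stable disease | partial response |
| Progression from | max(63.6, 58) = 63.6 mm | max(39.6, 38) = 39.6 mm |

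Suppose both lesions later measure 40 + 12 = 52 mm. Against 53 mm this is −1.9%, which is not progression. Against 33 mm it is +57.6% and +19 mm, which is progression.

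**When the response call changes.** With O the sum of the other target lesions and L the last value, the category differs only if O + L > 0.70 × S0 and O + 5 ≤ 0.70 × S0. In the illustration 0.70 × 65 = 45.5 mm, and 53 and 33 fall on either side.
- *Lesion already small at its last measurement.* Take one target lesion with a baseline of 10–60 mm and a last value of 5–10 mm, in 1 mm steps. The call changes in 10 of 306 combinations, all with a baseline of 10–14 mm.
- *Lesion unmeasurable at the first on-study scan.* The last value is then the baseline B. For a sole non-nodal target lesion (B ≥ 10 mm on CT), carrying forward gives 0% change and stable disease. The 5 mm entry gives a fall of (B − 5)/B ≥ 50% and a partial response. For B = 25 mm, progression starts at max(30, 30) = 30 mm rather than max(6, 10) = 10 mm.
- *Two target lesions.* One shrinks from 20 to 15 mm and then cannot be sized; the other stays at 30 mm. The sum is 45 mm of 50 (−10%, stable disease, progression from 54 mm) or 35 mm (−30%, partial response, progression from 42 mm).

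**When the progression call changes.** The carried-forward nadir is higher only if L > 5 mm.
- A sole lesion going from 30 to 8 mm is a partial response under both entries, with progression from 13 mm or 10 mm.
- A sole lesion going from 30 to 4 mm gives the same category and the same 9 mm threshold under both.

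Once the lesions can be measured again, the calls differ only at scans where the sum lies between the two thresholds, here from 39.6 up to 63.6 mm.

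**The case against.** The best defence is that section 2.2, read whole, already settles every case: real value if there is one, 0 mm if gone, 5 mm if present. It even explains why 5 mm is used. A reader who applies those specific sentences throughout introduces no bias, and the proposed rule only reorders text already on the page. This stands as far as it goes. But it requires the reader to set aside a sentence worded as essential in favour of one worded as optional, and the protocol never says to do so.

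The 0 mm sentence states its own condition and can fairly be read as an override. The conflict is therefore mainly with the 5 mm rule.

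A reader might also infer that the rule generally turns responses into stable disease, raises the nadir so that progression is missed, and biases the primary endpoint upward. The documents do not support that:

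- The response call changes only under the condition shown in the working. Many lesions stay a partial response under either entry.
- The nadir is not raised; it falls less than under the 5 mm default. Progression by target lesions is delayed while the sum lies between the thresholds.
- Progression by new or non-target lesions counts regardless of the sum.
- To alter the 1-year rate, a patient must progress by target lesions alone and the delay must span the one-year mark. No count of such patients can be derived.
- The illustration assumes that a 25 mm lesion becomes unmeasurable within six weeks. It shows what is possible, not how often. The protocol gives no depth of response for platinum-etoposide from which a frequency could be argued.

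The 10-of-306 count should not be taken as reassurance either. It assumes a last value of 5–10 mm and so leaves out larger last values, including most lesions that become unmeasurable by the first on-study scan.

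**Conclusion.** The contradiction is real, lies within one section, and sits in the text that the protocol makes its assessment method. If the last value is entered and exceeds 5 mm, the sum is larger than under the 5 mm default. ORR can then be understated and target-lesion progression called late, the latter in the direction that favours PFS and the 1-year PFS rate. The same scans can give opposite calls: 53 mm and stable disease or 33 mm and partial response, with progression from 63.6 or 39.6 mm, on assumed sizes.

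The size of the effect on any endpoint is unknown. One patient of 45 is 1/45 = 2.2 percentage points, but that holds for any misclassification and is not an estimate of this one. There is no effect if the last value is 5 mm or less, or if readers always apply the 0 mm and 5 mm sentences. The point deserves correction because a rule followed as written can give a wrong sum and the correction is very cheap, not because bias in the primary endpoint has been shown.

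**What to change.** Delete the carry-forward sentence from Appendix 3, section 2.2, and state one ordered rule built from the text already there:

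1. Record the actual measurement whenever one can be given, even below 5 mm.
2. If none can be given and the radiologist judges the lesion gone, record 0 mm.
3. If none can be given and the lesion is present, record 5 mm, worded as a requirement rather than an option.

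Put the same rule in the eCRF completion guidance. Check whether any sums were entered with a carried-forward value, and re-derive those that were; the documents give no sign either way. The cost is a short amendment, one edit to the guidance and a data check. No new scans are needed.

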2.3 Assessment of Non-target Lesions

This section defines the response criteria for non-target lesion tumors. Although some non-target lesions are actually measurable, they do not need to be measured; only a qualitative assessment is required at the time points specified in the protocol.

- Complete Response (CR): All non-target lesions disappear, and tumor markers return to normal levels. All lymph nodes are non-pathological in size (short-axis diameter <10 mm).
- Partial Response/Non-progressive Disease: The presence of one or more non-target lesions and/or persistent levels of tumor markers above normal levels.
- Progressive Disease: A clear progression of existing non-target lesions. Note: The appearance of one or more new lesions is also considered progressive disease.
- 2.4 Special Notes on the Assessment of Non-target Lesion Progression Supplementary explanations regarding the definition of progression of non-target lesions are as follows: When a patient has measurable non-target lesions, even if the target lesion assessment is stable or partially responsive, to define clear progression based on non-target lesions, the overall deterioration of non-target lesions must reach a level that necessitates termination of treatment. A general increase in the size of one or more non-target lesions is often not sufficient to meet the criteria for progression; therefore, defining overall tumor progression based solely on changes in non-target lesions when target lesions are stable or partially responsive is almost rare.

When a patient's non-target lesions are all non-measurable: This situation occurs in some Phase III trials where the inclusion criteria do not specify the presence of measurable lesions. The overall assessment still refers to the standards mentioned above, but since there are no measurable data for lesions in this case. The deterioration of non-target lesions is not easy to assess (by definition: all non-target lesions must indeed be unmeasurable), so when changes in non-target lesions lead to an overall increase in disease burden equivalent to that of disease progression in target lesions, defining clear progression based on non-target lesions requires the establishment of an

effective detection method for assessment. For example, an increase in tumor burden equivalent to a 73% increase in volume (equivalent to a 20% increase in the diameter of measurable lesions). Other examples include the progression of peritoneal exudate from "minimal" to "large amount"; lymphatic disease from "localized" to "widespread dissemination"; or described in the protocol as "sufficient to change the treatment method." Examples include the progression of pleural effusion from trace to large amounts, lymphatic involvement spreading from the primary site to distant sites, or possibly described in the protocol as "necessitating a change in the treatment approach." If clear progression is identified, the patient should be considered to have overall disease progression at that point. It is best to have objective criteria applicable to the assessment of non-measurable lesions, noting that the criteria for increase must be reliable.

